**SHR-1210:**

200 mg per cycle.

**Oxaliplatin:**

Scheduled dose per cycle = Total dose of this dosing (mg)

**Apatinib:**

Scheduled dose per cycle = Total dose of this dosing (mg)

**Capecitabine:**

Scheduled dose per cycle = Total daily scheduled dose  $\times$  Number of days the corresponding dose is used (days)

3) Subject compliance (%) = (Actual dose/Scheduled dose)  $\times$  100%.

All study drugs will be listed and analyzed by cohort, subject code, treatment stage, dosing date, and actual dose.

4) Duration of exposure to study drugs (weeks) = (Date of last dosing - Date of first dose + 1)/7.

Actual dose, scheduled dose, and compliance will be summarized by drug and cohort.

## 11.4 Safety Analysis

The safety analysis will be carried out based on the safety set by cohort.

### 11.4.1 Adverse event

An adverse event (AE) refers to any untoward medical occurrence in a study subject administered a medicinal product and which does not necessarily have a causal relationship with this treatment. In this study, AE should be collected from the signing of informed consent form (ICF) to 90 days after the last dosing of study drugs. AE includes any adverse symptom or sign, laboratory test abnormality, or disease. AE will be summarized separately in different stages of cohort 1 (SHR-1210 + capecitabine + oxaliplatin, sequence by SHR-1210 + apatinib mesylate, and total) and cohort 2.

AE will be analyzed based on treatment-emergent adverse event (TEAE). TEAE is defined as an AE that occurs or becomes aggravated on the same day or after the first dosing of study drugs but not later than 90 days after the last dosing of study drugs. Only TEAE will be summarized and analyzed. A separate data listing will be provided only for AE that occurs before treatment.

Each AE will be coded by MedDRA (v23.0) and graded by NCI-CTCAE v4.03. For the same SOC and/or PT, multiple cases of the same events that occur in one subject will be counted only once. For the same AE reported in one subject multiple times but varying in CTCAE grade, the greatest grade episode will be enumerated.

A summary description report will be provided for the number and percentage of subjects experiencing at least one TEAE, treatment-related TEAE (SHR-1210, oxaliplatin, capecitabine, and apatinib), severe TEAE (CTCAE Grade  $\geq 3$ ), TEAE leading to study drug discontinuation/interruption, treatment-related TEAE leading to drug discontinuation/interruption, TEAE leading to dose modification of study drugs, treatment-related TEAE leading to dose modification of the study drugs, TEAE leading to subject withdrawal from treatment, serious adverse event (SAE), and death.

In the TEAE summary table, AE occurring after the study drug treatment will be analyzed by MedDRA system organ class (SOC) and preferred term (PT), and descriptive statistics will be provided by frequency and percentage. The summary table contains the number of subjects experiencing at least one TEAE, TEAEs leading to treatment withdrawal, SAEs, TEAEs related to each study drug, and CTCAE Grade  $\geq 3$  treatment-related TEAE, along with CTCAE grades. After study drug treatment, each TEAE, SAE, TEAE of special interest, immune-related TEAE, and possible liver injury event, along with CTCAE grade, in each cohort will be summarized by SOC and PT, and each treatment-related TEAE and SAE related to study drugs will be summarized by SOC and PT. Immune-related AE will also be summarized by immune-related category and PT. The incidence of AE is calculated based on the number of subjects having an AE, instead of the number of AE episodes. For TEAE occurring after the start of study treatment, causality with study drugs consists of definitely related, possibly related, and indeterminable; if causality is missing, the TEAE will be considered drug-related for analysis. TEAE with CTCAE grade missing will be counted as missing.

TEAE of special interest includes the following:

- Grade  $\geq 3$  infusion reaction;
- Grade  $\geq 2$  diarrhea/colitis, uveitis, and interstitial pneumonia;
- Other Grade  $\geq 3$  immune-related AE;
- Grade 4 amylase or lipase increased.

Each AE, TEAE leading to dose interruption or modification, TEAE leading to treatment withdrawal, severe TEAE, and death will be listed.

For immune-related TEAE (classified by immune-related TEAE), the descriptive summary of the number and percentage of subjects have received corticosteroids or immunomodulators, received immunomodulators, received corticosteroids (further divided into systemic and topical administration), and received high-dose corticosteroids (defined as at least one dose or daily dose of  $\geq 40$  mg prednisone or equivalent; further divided into systemic and topical administration), and the starting dose and duration of high-dose corticosteroids will also be provided. The dosage of different hormonal drugs will be converted into the equivalent dose of prednisone according to the following formula: 0.75mg of dexamethasone = 5 mg of prednisone = 4mg of methylprednisolone = 20mg of hydrocortisone = 0.8mg of betamethasone.

If one subject experiences one AE and receives two or more hormones during the presence of the AE, the starting dose of the hormone used first will be involved in the statistics of starting doses (i.e., the starting dose(s) of subsequent hormone therapy/therapies will not be involved in the statistics of starting doses). Then, the cumulative duration of the use of multiple hormones (time overlapping of hormone therapies should be avoided in the calculation) will be summarized as the duration of dosing. If one AE category (such as the category of immune-related AE) contains more than one AE (by PT), this AE category will be treated as one AE when being summarized. When the initial dose is summarized, if the dosing frequency of hormones is more than once a day, it will be converted into a single daily dose before being summarized. When the duration of dosing is summarized, if the end date of hormone drug treatment is unknown, it will be imputed with the start date of the last dose of the hormone drug treatment.

Corrective treatment, site, maximum diameter, incidence of hemorrhage, and incidence of infection will also be summarized for reactive capillary endothelial proliferation.

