5.0	5 Jun., 2018	Updated the treatment of cohort 1. Updated the original treatment for cohort 1 (at least four cycles of SHR-1210 combined with capecitabine and oxaliplatin sequenced by SHR-1210 monotherapy as maintenance treatment) to the following: SHR-1210 + capecitabine + oxaliplatin for 4-6 cycles, followed by SHR-1210 + apatinib in the treatment of the subjects without disease progression. Based on the above revisions, relevant contents including the title of the study, were updated: The title was updated to "An Open-Label, Multi-Center, Phase II Study of Anti-PD-1 Antibody SHR-1210 Plus Capecitabine and Oxaliplatin Sequenced by SHR-1210 with Apatinib Mesylate or Apatinib in Patients with Previously Untreated Advanced or Metastatic Gastric (GC) or Gastroesophageal Junction (GEJ) Cancer"; The study objectives were updated to "Primary objective: To evaluate the efficacy of the sequential therapy of SHR-1210 combined with capecitabine and oxaliplatin or SHR-1210 combined with apatinib mesylate as the first-line therapy for advanced or metastatic gastric (GC) or gastroesophageal junction (GEJ) cancer"; Secondary objective: "To evaluate the safety of the sequential therapy of SHR-1210 combined with capecitabine and oxaliplatin or SHR-1210 combined with apatinib mesylate for the treatment of advanced or metastatic gastric (GC) or gastroesophageal junction (GEJ) cancer". According to the latest CDE requirements on drug safety, relevant contents in the study were updated: a) AEs: AEs are recorded from the date of signing informed consent to the end of the safety follow-up (90 days after the last dose) or the start of a new anti-cancer therapy. b) Death caused by the symptoms and signs of PD will be reported as an SAE. c) "Definitely related", "possibly related" and "unlikely related" and "indeterminable" are all listed as adverse drug reactions. d) The collection and follow-up duration of AE/SAE are reinforced (see section 7.4.1). e) The CFDA and the National Health and Family Planning Commission have changed to other names but the GCP and Provisions for Drug Registration have not been updated yet. Therefore, the reporting of SAEs was updated: "The SAE must be reported to the relevant regulatory authorities, the sponsor, and the ethics committee within 24 hours of knowing of the event. The sponsor's email address for safety data is: [contact] ."
-----	--------------	--

6.0 8 Aug., 2018

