1. The safety data by 7 Aug., 2018 showed that the safety and tolerance of SHR-1210 combined with apatinib (500 mg/d) were poor: Among 11 patients receiving SHR-1210 + apatinib treatment, there were 4 SAEs related to apatinib (including grade 3 transaminase increased, grade 3 erythema multiforme, grade 3 upper gastrointestinal hemorrhage, and grade 4 skin toxicity). By referring to the latest data from other studies of SHR-1210 plus apatinib treatment and after discussion with PI, it is planned to reduce the dose of SHR-1210 plus apatinib to 375 mg/d. For more details, see section 5.1.5 Regimen of the drugs.

Section 5.2.3 Dose Modification of Apatinib Mesylate has also been updated accordingly based on the above changes in the dose of apatinib: Depending on the initial dose of apatinib, the dose of apatinib mesylate can be reduced to 375 mg qd or 250 mg qd.

2. Blood sampling for Pharmacokinetic study and for anti-drug antibodies were added to fully investigate the properties of SHR-1210 combined with apatinib and to more effectively analyze the safety and efficacy of the combined treatment (see section 3.1).
3. Blood sampling burden is minimized as much as possible for the subjects based on the current medical practice while satisfying the medical requirements. For the HBV DNA test, the following requirement was proposed: If the Hepatitis B five items test indicates HBV infection [HBsAg positive] or a history of HBV infection, HBV DNA quantification shall be performed (see section 6.1).
4. Capecitabine (0.15 g/tablet) and oxaliplatin (100 mg/bottle) were added to facilitate the subjects to receive the study drug based on the current medical practice (see section 5.1.2).
5. In section 5.2.3 Dose Modification of Apatinib Mesylate, "dose delay" was revised to "dose interruption" to improve the correctness of description.
6. In section 7.4.5 Pregnancy Report, reporting to the ethics committee was added with improvement of wording: "Female subjects who become pregnant during the study must withdraw from the study. If a female partner of a male subject becomes pregnant, the male subject will continue participation in the clinical study. The investigators must fill out the "Pregnancy Report/Follow-up Form for Hengrui's Clinical Studies" and report to the sponsor within 24 hours after becoming aware of the pregnancy, and report to the ethics committee promptly".

SPONSOR'S SIGNATURE PAGE

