5.1.5 Administration of study drugs

SHR-1210

SHR-1210, intravenous infusion at a fixed dose of 200 mg over 30 min (the total infusion time should be no less than 20 min and no more than 60 minutes, including rinsing period), once every 3 weeks.

Apatinib Mesylate Tablets

375 mg, administered orally once daily. Administered with warm water approximately half an hour after meals (administration time should be the same in each day whenever possible).

Capecitabine

1000 mg/m², administered orally twice daily 30 min after meals (once in the morning and once in the evening; with a total daily dose of 2000 mg/m²). Two weeks of treatment is followed by 1 week of rest period (i.e., drug administration from Day 1 to Day 14, and drug interruption from Day 15 to Day 21) in 3 week cycle.

Oxaliplatin

130 mg/m², intravenous infusion with 250-500 mL of 5% glucose solution, given over 2-6 h; administered on Day 1 of each treatment cycle, once every 3 weeks.

SHR-1210 will be administered intravenously followed by oxaliplatin at least 30 min interval on Day 1 of each cycle.

Study Treatment	Drug	Treatment Cycle (21 days)	
Cohort 1	SHR-1210 200 mg	Day 1	
	Capecitabine 1000 mg/m ²	Day 1-Day 14	4-6 cycles
	Oxaliplatin 130 mg/m ²	Day 1	
	SHR-1210 200 mg	Day 1	
	Apatinib 375 mg	Day 1-Day 21	
Cohort 2	SHR-1210 200 mg	Day 1	
	Apatinib 375 mg	Day 1-Day 21	

Table 6. Administration plan of the study drugs

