5.2.3 Dose modification of apatinib mesylate

Dose modifications caused by apatinib-related toxicities include the following: treatment interruption (no more than 28 days), dose reduction (to 375 mg qd or 250 mg qd, depending on the initial dose of apatinib), and permanent discontinuation.

The treatment may be delayed and the dose be reduced for Grade ≥ 3 hematologic toxicity or ≥ 2 non-hematologic toxicity; for non-hematologic toxicity, manageable nausea and vomiting, and fever (below 38 $^{\circ}\text{C}$) of determined cause, active symptomatic treatment can be administered first. There is no need to immediately delay the treatment or reduce the dose.

In case of apatinib-related toxicity, administration should be delayed until recovery, and then the original dose should be resumed or the dose should be reduced by one dose level. The minimum dose allowable is 250 mg/d. If the dose is still intolerable at the reduced dose of 250 mg/d, apatinib should be permanently discontinued (refer to [Table 9](#) for the recommended dose modification method). Dose increase of apatinib is not allowed during the study period.

Table 9. Recommended dose modification of apatinib

Apatinib-Related Toxicities	Grade	Dose Delay or Not	Criteria for Resuming	Dose Modification Method	Criteria for Discontinuation
Hematologic Toxicity	Grade 1-2	No	—	—	—
	Grade 3	Yes	Until the toxicity recovers to Grade ≤ 2	Resume at original dose	Apatinib interruption for more than 28 days
	Grade 4		Until the toxicity recovers to Grade ≤ 2	Reduce the dose by one level	
Non-Hematologic Toxicity	Grade 1	No	—	—	—
	Grade 2 (last for ≥ 7 days)	Yes	Until the toxicity recovers to Grade ≤ 1	Resume at original dose	Apatinib interruption for more than 28 days
	Grade 3	Yes	Until the toxicity recovers to Grade ≤ 1	Reduce the dose by one level	
Hypertension	Grade 3 (after corrective treatment)	Yes	Until the toxicity recovers to Grade ≤ 1	Reduce the dose by one level	Apatinib interruption for more than 28 days
Proteinuria (without significant increase in blood creatinine)	Grade 3 (24-h urine protein quantification)	Yes	Until the toxicity recovers to Grade ≤ 2	Reduce the dose by one level	Apatinib interruption for more than 28 days

Apatinib-Related Toxicities	Grade	Dose Delay or Not	Criteria for Resuming	Dose Modification Method	Criteria for Discontinuation
Hand-and-Foot Syndrome	Grade 3	Yes	Until the toxicity recovers to Grade ≤ 1	Reduce the dose by one level	Apatinib interruption for more than 28 days

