## 2 PROTOCOL AMENDMENT

Added overall survival (OS), time to objective response (TTOR), and subgroup analysis as exploratory efficacy analysis to provide guidance for subsequent phase III clinical studies

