## 6 ANALYSIS SETS

### 6.1 Full Analysis Set (FAS)

It includes all subjects who are randomized and have received study drugs at least once. This analysis set will be used for the efficacy analysis.

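### The planned AE tables are not split by apatinib starting dose, so apatinib-period rates can mix 500 mg/d with 375 mg/d and do not show the rate at 375 mg/d

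*SAP*

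**What the plan says.** Two starting doses are documented.

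- The protocol's version 6.0 amendment entry calls the combination with apatinib at 500 mg/d poorly tolerated: "Among 11 patients receiving SHR-1210 + apatinib treatment, there were 4 SAEs related to apatinib" by 7 August 2018. It then brings in outside evidence separately ("By referring to the latest data from other studies of SHR-1210 plus apatinib treatment and after discussion with PI") and lowers the dose to 375 mg/d.
- Current protocol 5.1.5 gives one apatinib dose: "375 mg, administered orally once daily".
- Current protocol 5.2.3 allows "dose reduction (to 375 mg qd or 250 mg qd, depending on the initial dose of apatinib"). A reduction to 375 mg makes sense only for someone who started higher.

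The SAP keeps all these subjects and groups them without regard to dose.

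- The FAS (SAP 6.1) is defined as follows: "It includes all subjects who are randomized and have received study drugs at least once". The safety set (SAP 6.3) has no dose restriction either.
- For safety, SAP 11.4.1 says "AE will be summarized separately in different stages of cohort 1" (chemotherapy phase, apatinib phase, total), with cohort 2 as one group.
- SAP 11.5 summarises ORR by Simon stage and cohort. None of the nine subgroup factors in SAP 11.5.3.3 is apatinib dose, and they apply only to ORR, PFS and OS.
- Dose appears only in the exposure and compliance outputs of SAP 11.3, which are not crossed with AEs.

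**The concern.** Safety is the study's secondary objective (protocol 2.1, SAP 3.2.2). The SAP already separates the two phases of cohort 1, so it accepts that an AE rate should belong to the treatment being taken. The same reasoning applies to dose: 500 mg/d was given up because of toxicity, and 375 mg/d is the regimen the protocol now describes. A reader of the cohort 2 table, or of the cohort 1 apatinib-phase column, would naturally take the rates as those of 375 mg/d. If a meaningful share of the column started at 500 mg/d, they are not, and nothing in the planned tables would show it.

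**Working it through.** **1. The design figure, which is not in dispute.** For cohort 2 (19 subjects with at least 4 responses, then 55 with at least 13), the exact rejection probability is Σ over x = 4 to 19 of Bin(x; 19, p) × P[Bin(36, p) ≥ 13 − x]. This gives 0.0477 at p = 0.15 and 0.8006 at p = 0.30, which matches the stated 0.05 and 80%. Splitting an AE table leaves both unchanged.

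**2. Inputs for the mixing.**
- From the version 6.0 entry: 11 patients and 4 related SAE events. The wording sets these data apart from other studies, so the 11 are read as this trial's patients.
- From protocol 8.2: cohort 2 has n = 55.
- Not stated, so varied: k, the number of the 11 in cohort 2; s, the number of subjects with the 4 events (SAP 11.4.1 counts subjects, the amendment entry counts events); and t, the true related-SAE rate at 375 mg.
- Assumed: no subject started at 500 mg after 7 August 2018.

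**3. Formula.** With rate s/11 in the 500 mg starters, the expected pooled cohort 2 rate is [k × s/11 + (55 − k) × t] / 55. The gap from the 375 mg rate is therefore (k/55) × (s/11 − t). It is zero at k = 0 and negative when t exceeds s/11, which is 9.1%, 18.2% or 36.4% for s = 1, 2 or 4.

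**4. All 11 in cohort 2 (k = 11, or 11/55 = 20%).** The pooled rate is (s + 44t)/55:

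| t | s = 1 | s = 2 | s = 4 |
|---|---|---|---|
| 5% | 3.2/55 = 5.8% | 4.2/55 = 7.6% | 6.2/55 = 11.3% |
| 15% | 7.6/55 = 13.8% | 8.6/55 = 15.6% | 10.6/55 = 19.3% |
| 25% | 12/55 = 21.8% | 13/55 = 23.6% | 15/55 = 27.3% |

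The gap runs from +6.3 points (t = 5%, s = 4) to −3.2 points (t = 25%, s = 1).

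**5. Fewer of the 11 in cohort 2 (s = 4, t = 5%).** For k = 0, 4, 6 and 11 the pooled rate is 5.0%, 7.3%, 8.4% and 11.3%.

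**6. What is known about k.** Until version 5.0 (5 June 2018), cohort 1 chemotherapy was "sequenced by SHR-1210 monotherapy as maintenance treatment", without apatinib. From 5 June to 7 August is 63 days, and four 21-day cycles take 84. Cohort 1 could therefore contribute to the 11 only through subjects already on treatment who moved to apatinib. That makes a low k less likely but does not fix it.

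**7. The remainder falls in cohort 1.** Any of the 11 not in cohort 2 enter the cohort 1 apatinib-phase column. For example, with 5 of them there, s = 4, t = 5%, and 20 to 43 subjects assumed to reach that phase, the pooled rate is (5 × 4/11 + 15 × 0.05)/20 = 12.8% down to (5 × 4/11 + 38 × 0.05)/43 = 8.6%.

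**The case against.** The sponsor has several fair answers.

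- **The split can be recovered from listings.** SAP 11.4.1 lists each AE, and SAP 11.3 lists dosing date and actual dose by subject. This stands: what is missing is a pre-specified table, not data. But a split chosen after the tables are seen carries less weight than one planned before lock.
- **The protocol has another route to the dose question.** Protocol 8.4.4 plans to relate drug exposure to toxicity. SAP 11.6, however, specifies only descriptive concentrations. PK sampling also came in with version 6.0, the amendment that cut the dose, so early 500 mg subjects may have no samples. It does not replace an AE table by dose.
- **The arithmetic rests on unknowns.** This stands. Even four affected subjects among 11 gives a 95% Clopper-Pearson interval of 10.9% to 69.2%. Relatedness may also be defined differently: protocol 7.3.2 counts unlikely-related events as drug reactions, SAP 11.4.1 does not, and the amendment entry does not say which rule its 4 SAEs followed.

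Two stronger readings are tempting, and neither is supported.

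- A reader might tie the point to phase III planning through SAP 2. That section gives "subgroup analysis as exploratory efficacy analysis to provide guidance for subsequent phase III clinical studies" (with OS and TTOR) as its additions, which are efficacy analyses. It says nothing about safety tables, and no phase III dose is named.
- A reader might infer that ORR is distorted, or that the SAP dropped an ORR split promised in protocol 8.4.2, which speaks of summarising by stage and dose group. No dose effect on ORR is shown anywhere. The next sentence of 8.4.2 says treatment group, so the term may simply mean cohort.

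**Conclusion.** The point holds as a gap in safety reporting. The documents show two apatinib starting doses, the analysis sets keep both, and no planned AE table separates them. The tables therefore cannot give the AE rate at 375 mg/d.

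The size cannot be determined. With all 11 in cohort 2 and a 5% rate at 375 mg, the pooled related-SAE rate lies between 5.8% and 11.3%, depending on how many subjects had the 4 events. It is unaffected if none of the 11 were in cohort 2, and it can fall below the 375 mg rate when that rate is high. A reader might conclude that the reported rates will be inflated or doubled; that holds only in the most adverse corner of the range. These figures assume that the 11 were this trial's patients and that no one started at 500 mg after the cut-off. The documents also do not say whether ongoing 500 mg subjects were moved to 375 mg.

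The primary endpoint, the decision rules and their error rates are untouched. This is a cheap improvement, resting on the secondary safety objective alone.

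**What to change.** In SAP 11.4.1, add that at the final analysis the overall TEAE, related Grade ≥ 3 TEAE and related SAE tables for the SHR-1210 + apatinib period are shown within cohort by apatinib starting dose (500 mg, 375 mg, total). Define starting dose as the first apatinib dose in the SAP 11.3 dosing records. Flag 500 mg starters later reduced to 375 mg, because their column mixes exposures.

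A descriptive cohort 2 ORR by starting dose is optional. The sponsor should confirm whether dose group in protocol 8.4.2 means dose or cohort; if it means dose, SAP 11.5 should carry the split.

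The cost is a few extra table columns from dosing data already planned for listing. It needs no new data or interim output and leaves the sample size and the 4/19 and 13/55 rules as they are. The downside is a 500 mg column that is small, imprecise and descriptive only, and it should be labelled so.

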5.2 Dose Modification of Study Drugs

5.2.1 Dose modification of SHR-1210

Dose increases and reductions of SHR-1210 are not permitted. If SHR-1210 treatment is interrupted due to a toxicity, the subject may resume the treatment at the original dose after the toxicity is resolved. AEs related to SHR-1210 may be immune toxicities, and may occur shortly after the first dose or several months after the last dose. If the conditions listed in [Table 7](#) occur, the use of SHR-1210 should be interrupted. During the study, the investigator must consult with the sponsor if the investigator considers that an adjustment listed in [Table 7](#) is inappropriate based on the benefit-to-risk ratio of subjects or that SHR-1210 treatment should be interrupted or resumed due to a condition not listed in the table.

Table 7. Dose modification criteria for SHR-1210 due to immune-related toxicity

SHR-1210-Related Toxicity	Grade for Interruption	Resumption	Discontinuation
Diarrhea/Colitis	Grade 2-3	Recovered to Grade 0-1	Toxicity has not resolved by 12 weeks after the last dose, or the corticosteroid dose cannot be reduced to prednisone 10 mg/day (or equivalent) or lower within 12 weeks after the last dose.
	Grade 4	Discontinuation	Discontinuation
AST/ALT or Bilirubin Increased	Grade 2	Recovered to Grade 0-1	Toxicity has not resolved by 12 weeks after the last dose, or the corticosteroid dose cannot be reduced to prednisone 10 mg/day (or equivalent) or lower within 12 weeks after the last dose.
	Grade 3-4	Discontinuation ^a	Discontinuation
Type 1 Diabetes Mellitus (new onset) or Hyperglycemia with Signs of β-cell Failure	Grade 3-4 or new-onset type 1 diabetes	SHR-1210 treatment may only be resumed after the clinical and metabolic conditions of the subject are stabilized.	
Hyperthyroidism	Grade 3	Toxicity reduced to Grade 0-1	Toxicity has not resolved by 12 weeks after the last dose, or the corticosteroid dose cannot be reduced to prednisone 10 mg/day (or equivalent) or lower within 12 weeks after the last dose.
	Grade 4	Discontinuation	Discontinuation
Hypothyroidism	Grade 2-4	Study treatment can be continued after starting thyroxine replacement therapy	

SHR-1210-Related Toxicity	Grade for Interruption	Resumption	Discontinuation
Pneumonia	Grade 2	Toxicity reduced to Grade 0-1	Toxicity has not resolved by 12 weeks after the last dose, or the corticosteroid dose cannot be reduced to prednisone 10 mg/day (or equivalent) or lower within 12 weeks after the last dose.

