7.4 Follow-up and Reporting of Adverse Events

7.4.1 Follow-up of AEs/SAEs

All AEs/SAEs should be followed up until they are resolved, return to baseline levels or Grade ≤ 1 , reach a stable state, or are reasonably explained (e.g., lost to follow-up, death).

During each visit, the investigator should ask about the situation of AEs/SAEs that occur after the last visit and provide follow-up information in a timely manner based on the sponsor's query request. Principles of collection and follow-up of AEs/SAEs after the last dose at the end of treatment are shown in the table below.

Table 14. Requirements for collection and follow-up of AEs/SAEs

Classification	Collection/Documentation Requirements	Follow-Up Requirements
Unrelated AEs	Until the end of safety follow-up period or start of a new anti-tumor treatment (whichever comes first)	Until the end of safety follow-up period
Treatment-related AEs	Until the end of safety follow-up period	Until resolved, remission, or recovered to baseline levels or Grade ≤ 1 , steady state, or reasonably explained (e.g., lost to follow-up, death).
Unrelated SAEs (including SIEs)	Until the end of safety follow-up period or start of a new anti-tumor treatment (whichever comes first)	Until the end of safety follow-up period
Treatment-related SAEs (including SIEs)	No time limit	Until resolved, remission, or recovered to baseline levels or Grade ≤ 1 , steady state, or reasonably explained (e.g., lost to follow-up, death).

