7.4.3 Reporting of serious adverse events

Serious adverse events (SAEs) that occur from the signing of the informed consent form until 90 calendar days (inclusive) after the last dose will be collected. In the event of an SAE, whether it is an initial report or a follow-up report, the investigator must complete the "NMPA Serious Adverse Event Report Form" immediately, with a signature and date. It must have been reported to the relevant regulatory authorities, the sponsor, and the ethics committee within 24 hours of knowing of the event.

The sponsor's email address for safety data is: [contact].

SAEs that occurred 90 days after the last study dose were generally not reported unless they were suspected to be related to the study drugs. The symptoms, severity, causality with the study drug, time of onset, time of treatment, measures taken, time and method of follow-up, and outcome should be documented in detail in the SAE report. If the investigator believes that an SAE is not related to the study drug but potentially related to the study conditions (such as the discontinuation of past treatment, or comorbidities during the study), the causality should be explained in the description section of the SAE report form. If the severity of an ongoing SAE or its relationship to the study drug changes, a follow-up report should be submitted immediately. If an error is found in a previously reported SAE, such SAE may be revised, revoked, or downgraded in follow-up reports and reported in accordance with the SAE reporting procedure.

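### The SAP gives no defined summary to treatment-related SAEs with onset more than 90 days after the last dose, although the protocol collects them without a time limit

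*SAP*

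**What the plan says.** **SAP 11.4.1** sets one window in three steps.
- Collection: "AE should be collected from the signing of informed consent form (ICF) to 90 days after the last dosing of study drugs". No exception is made for related SAEs.
- Definition: a treatment-emergent event starts or worsens on or after the first dosing day, "but not later than 90 days after the last dosing of study drugs".
- Analysis: "Only TEAE will be summarized and analyzed". For events outside the window, the only extra output named concerns the time before treatment: "A separate data listing will be provided only for AE that occurs before treatment".

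**The protocol** goes further for one class of event.
- Section 5.2.1 says that SHR-1210-related events may be immune toxicities and "may occur shortly after the first dose or several months after the last dose".
- Table 14 in section 7.4.1 sets no time limit on collecting treatment-related SAEs, and counts special-interest events in that row.
- Section 7.4.3 says SAEs later than 90 days after the last dose are generally not reported "unless they were suspected to be related to the study drugs".

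Section 2.2 makes the incidence and severity of AEs and SAEs a secondary endpoint and attaches no 90-day limit to it.

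**The concern.** The protocol recognises that harm from SHR-1210 can be delayed and keeps collection open for related serious cases. The SAP's general rule then restricts summaries to a window that closes at day 90. A related immune SAE starting on day 120 would be in the database, but under that rule it would not be counted in any incidence table.

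The effect runs in one direction: leaving out collected related SAEs can only lower the count reported for this secondary endpoint. There is also a reproducibility problem. Because the SAP is not consistent about which items carry the treatment-emergent label, two programmers could apply different windows to the SAE and death rows and both claim to have followed the plan.

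**Working it through.** The plan states no figure to reproduce, so the main check is a comparison of texts.

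**Step 1. Which events fall between the documents?**

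| Event class | Protocol collection | SAP summary |
|---|---|---|
| Non-serious AE, related or not | At most to the end of safety follow-up (90 days) | To 90 days |
| Unrelated SAE | At most to the end of safety follow-up | To 90 days |
| Treatment-related SAE, including special-interest events | No time limit (Table 14; 7.4.3) | To 90 days under the general rule |

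Only the last row is mismatched.

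**Step 2. Does the SAP's detail reopen the window?** The special-interest, immune-related and steroid-use summaries in 11.4.1 are described as treatment-emergent. The overview list, however, ends with SAE and death without that label. The tables by system organ class and preferred term include SAEs and drug-related SAEs without it, and one sentence on immune-related AEs by category also omits it. None of these items states a later cut-off, and the general rule in the same section is categorical. The plain reading is therefore 90 days throughout, but it is not the only possible reading.

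**Step 3. Could a late event appear elsewhere?** The section also says each AE and each death will be listed. A late related SAE may therefore be visible in a listing, but a listing gives no incidence.

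**Step 4. How large might the gap be?** The documents give no rate of related SAEs after day 90. As an illustration, let p be the assumed proportion of subjects with such an event and n the number treated. Expected subjects omitted = n × p. Chance of omitting at least one = 1 − (1 − p)^n. The n values are the planned 43 and 55, and 43 + 55 = 98.

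| n | p = 0.5% | p = 1% | p = 2% |
|---|---|---|---|
| Cohort 1, 43 | 0.194 | 0.351 | 0.581 |
| Cohort 2, 55 | 0.241 | 0.425 | 0.671 |
| Both, 98 | 0.388 | 0.627 | 0.862 |

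For 98 subjects, for example, 1 − 0.99^98 = 0.627. The expected number of subjects omitted is 98 × 0.005 = 0.49, 98 × 0.01 = 0.98 and 98 × 0.02 = 1.96. With the enrolment allowance in protocol 8.2 (48 + 62 = 110), the chances are 0.424, 0.669 and 0.892.

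**The case against.** The strongest defence is that 90 days is the protocol's own window. Footnote 20 of the activity schedule, sections 7.2.2 and 7.4.2, and the first sentence of 7.4.3 all use it, so the SAP sentence repeats protocol text. Part of the delayed period described in 5.2.1 also falls inside 90 days. A table defined to day 90 makes no claim about day 120: its incidence is bounded rather than wrong. Late events are passively reported with no fixed observation period, so mixing them into the main tables would make rates harder to interpret. All of this stands, and it is why the 90-day tables should not be changed. It does not remove the gap for related SAEs, where Table 14 and the exception in 7.4.3 go beyond 90 days and the SAP is silent.

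Four stronger readings are tempting but not supported.
- **A reader might infer that late events vanish from every safety output.** The unlabelled SAE, related-SAE, immune-related AE and death items, and the listing of each AE, leave that open.
- **A reader might take the AE mark in the survival follow-up column as proof of monthly AE collection.** Footnote 20 ends AE recording at the end of safety follow-up or at new therapy. Footnote 24 and section 6.4.2 say the monthly contact gathers survival and subsequent treatment.
- **A reader might want the steroid-use tables extended.** Footnote 21 and section 5.5 stop recording concomitant medication at the end of safety follow-up, so those data are not planned for late events.
- **A reader might express the loss as a share of SAEs**, scaling the 38 SHR-1210-related SAEs in 539 patients (38/539 × 98 = 6.9). Those are events rather than subjects, they cover one drug given alone or in combinations, and nothing says how many were late.

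**Conclusion.** The point holds in limited form. Applied as written, the SAP's general rule leaves treatment-related SAEs with onset after day 90 collected but not summarised, and the wording of several items leaves their window unclear. The conclusion rests on the texts alone and needs no event rate.

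The size is unknown. The 39% to 86% chance of omitting at least one of 98 subjects depends wholly on assumed per-subject rates of 0.5% to 2%, and treats subjects as independent with all 98 treated. It shows that an omission is plausible at low rates; it does not forecast one. The matter affects the completeness of a descriptive safety endpoint and has no bearing on the ORR decision rules. It is worth correcting because the correction is cheap.

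**What to change.** In SAP 11.4.1:
1. Keep the 90-day treatment-emergent tables unchanged.
2. Add one summary, by cohort, system organ class and preferred term, giving the number and percentage of subjects with a treatment-related SAE or special-interest event starting more than 90 days after the last dose. Footnote that these events are passively reported without a fixed observation period, so the percentages are not comparable with the 90-day tables. State whether non-serious special-interest events are included, since the Table 14 row can be read either way.
3. State for the SAE, related-SAE, immune-related AE and death items whether they stop at day 90.
4. Reconcile the SAP collection sentence with Table 14 and section 7.4.3 of the protocol, and note the general 90-day statements elsewhere in the protocol.
5. Do not extend the steroid-use tables.

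The cost is a few SAP sentences and one short table. It uses SAE data the protocol already collects and adds no visit or procedure. The downside is interpretive: a small, passively ascertained count that must be read with its footnote.
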